## **XI. Immunogenicity Assessments**

The analyses described in this section will be performed at CR Medicon.

Subjects who received placebo will be combined into 1 treatment group for purposes of analysis.

Serum samples for the antibody assays will be collected at Day 1, 4, 7, 15, 30, 90 and EOS/180. Additionally, subjects who do not complete all required visits or withdraw from the study early are required to complete End-of Study/Early-Termination assessments. The serum samples for antibodies will be assayed for neutralizing antibodies.

Immunogenicity will be evaluated using descriptive statistics. The number and percentage of subjects for ADA and neutralizing antibodies results will be summarized by treatment at scheduled time point as well as all post-baseline visits. Percentages for the neutralizing antibody result are based on the number of positive ADA results at that visit. ADAnalysisA titers of subjects who becomes antibody positive will be summarized by treatment and cohort as received along with nominal collection time. Summary statistics including n, min, max, mean and median will be calculated. In addition, incidence of early and delayed-type hypersensitivity responses will be summarized by ADA results (positive or negative) and by treatment.

Antibody information of subjects will be presented in the form of data listings.

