**Table 3 Study Objectives and Endpoints**

Objectives	Endpoints
Primary	

Assess the safety and tolerability profile, including immunogenicity, of JK07, administered IV according to protocol-defined dosing regimen.

	

Incidence and severity of TEAEs and their relationship to the IP.

12-lead ECG parameters (heart rate, PR, QRS, QT, QTcF) change from baseline derived as mean from triplicate ECG recordings as well as QT and QTcF outlier analyses.

Change from baseline in the incidence of rhythm abnormalities (retrieved from telemetry readings for 48 hours postdose).

Laboratory parameters – change from baseline each assessment time point per Table 1 SoA postdose: hematology, chemistry, coagulation, and lipid panels.

Immunogenicity

Incidence of early and delayed-type hypersensitivity responses.

Presence of serum anti-JK07 antibodies (confirmed positive antibody response, titer, neutralizing antibodies).

Vital signs – change from baseline in vital signs and the relationship to JK07 compared with placebo, including:

Blood pressure (BP)

Temperature

Heart rate (HR)

Respiratory rate (RR)

Secondary	

To determine the PK characteristics of JK07 administered IV according to protocol-defined dosing regimen.

	

PK parameters of intact JK07 including, but not limited to, maximum concentration (<math>C_{max}</math>), time to <math>C_{max}</math> (<math>t_{max}</math>), area under the concentration-time curve to the last quantifiable concentration and extrapolated to infinity [<math>AUC_{(0-\text{last})}</math> and <math>AUC_{(0-\infty)}</math>], half-life (<math>t_{1/2}</math>), elimination rate constant (<math>\lambda_z</math>), systemic clearance (CL), and volume of distribution (<math>V_z</math>). Surrogate measurement of intact JK07 to be carried out through detection of both the JK07 antibody domain and the JK07 NRG-1 peptide fragment in the evaluation of PK parameters.

Exploratory	

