## 4.0 STUDY DESIGN

### 4.1 Overall Design

This is a phase 1, randomized, double-blind, placebo-controlled, single-ascending dose study to assess the safety, tolerability, immunogenicity, and PK of JK07 in HF subjects 18 to 80 years of age with LVEF  $\leq 40\%$ .

To be eligible for this trial, subjects must have been maintained on an optimal HF medical regimen for at least 2 months prior to informed consent and remain on the same treatment regimen throughout the course of the study, per the 2017 American College of Cardiology/American Heart Association Task Force on Clinical Practice Guidelines/Heart Failure Society of America (ACC/AHA/HFSA) treatment guidelines (Yancy et al, 2017).

Subjects will give informed consent prior to initiation of screening procedures. During screening, all subjects will undergo 2D-TTE to measure the following parameters: left ventricular chamber dimensions, including LVESV and left ventricular end diastolic volume (LVEDV), LVEF, and multiple calculated monitoring parameters using velocity and flow measurements (i.e., stroke volume [SV], cardiac output [CO], derived left ventricular filling pressure (E/e')) according to the American Society of Echocardiography guidelines (full set of measurements provided in [Section 11.0](#), Appendix 5). Subjects will also undergo a physical examination, 12-lead ECG assessment, blood sampling for laboratory parameters, and urine testing. Safety assessments at screening will include hematology, biochemistry, coagulation, liver, and thyroid function. There will be additional blood sample collection prior to IP administration for baseline myocardial biomarkers, PK, and immunogenicity assessment (Table 1).

A Data Review Committee (DRC) will be established to review emerging data, to monitor safety aspects of the study, to select the JK07 dose during dose escalation, and to adapt the randomization scheme. The DRC will evaluate the emerging clinical, laboratory and cardiac safety data, from the first three days postdose for the sentinel subject, prior to randomized blinded IP administration in the remainder of the cohort.

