### **8.2.8 Immunogenicity Assessments**

Antibodies to JK07 will be evaluated in serum samples collected from all subjects according to the Table 1 SoA. Additionally, serum samples should also be collected at the final visit from subjects who discontinued study treatment or were withdrawn from the study. These samples will be tested by the Sponsor or Sponsor's designee.

Serum samples will be screened for antibodies binding to JK07. Samples which show a positive response in the screening assay will be evaluated using a confirmatory ADA assay, and the confirmed positive samples will be reported and their potential for neutralizing activity will be explored. Other analyses will be performed to verify the stability of JK07 and to further characterize the immunogenicity of JK07.

The detection and characterization of antibodies to JK07 will be performed using a validated assay method by or under the supervision of the Sponsor. Antibodies may be further characterized and/or evaluated for their ability to neutralize the activity of the study treatment(s). Samples may be stored for a maximum of 10 years (or according to local regulations) following the last subject's last visit for the study at a facility selected by the Sponsor to enable further analysis of immune responses to JK07.

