#### **9.4.3 Safety Analyses**

All safety analyses will be performed on the Safety Population.

All safety data will be listed according to treatment group, subject number, and visit.

The AEs are defined in [Section 8.3.1](#). The DLAE are defined in [Section 4.6](#).

AEs will be coded using the Medical Dictionary for Regulatory Activities (MedDRA) Version 22. The number of AEs and incidence rates will be tabulated by preferred term and system organ class.

The AEs will be coded by maximum severity, relationship to study treatment, as SAEs or DLTs as needed, and will be categorized and tabulated for each treatment group (cohort).

DLAEs will be presented in the same manner as the AEs.

Incidence of injection site reactions will be summarized by treatment group, and if appropriate by assessment time.

All laboratory test results, vital signs measurements, ECG results, weight, and body mass index will be summarized for each treatment group using descriptive statistics at each visit for raw numbers and change from baseline. The incidence of treatment-emergent abnormal laboratory, vital sign, and ECG values will also be summarized using descriptive statistics.

For 12-lead ECG parameters (HR, PR, QRS, QT, QTcF), the 90 % confidence interval will also be presented for each parameter mean and change from baseline values. Outliers for QT and QTcF defined under outcome measures will be summarized using counts and percentages by treatment and sampling time, if appropriate and using subject-level maximum over time by treatment. The following categories will be presented by treatment and overall, for JK07:

- outlier QT and QTcF intervals (450-480 ms, 480-500 ms and >500 ms)
- change from baseline in QT and QTcF intervals (30-60 ms and >60 ms)

Additional corrections to QT may also be similarly analyzed. If relevant, analysis excluding ECGs capturing paced beats will be performed.

Abnormal findings on 12-lead ECG will be summarized by treatment using descriptive statistics.

All recorded ECGs will be interpreted on site and subsequently collected, digitized, and sent for central laboratory standardized measurements. The incidence (number of subjects and percent) of a confirmed positive ADA response will be summarized by treatment. The incidence of neutralizing anti-drug antibody response will also be summarized, if appropriate.

All data will be provided in data listings sorted by treatment group, subject number, and visit.

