### **B. Definition of Baseline**

This is a single-dose study. Unless otherwise specified, baseline is defined as the last non-missing measurement prior to study IP administration. Change from baseline will be calculated as post-baseline values minus baseline values.

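### The overall post-baseline ADA incidence, which reports a primary endpoint, has no rule separating antibodies already present before dosing from those that arise or rise afterwards

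*SAP*

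**What the plan says.** Protocol Table 3 lists among the primary endpoints "Presence of serum anti-JK07 antibodies (confirmed positive antibody response, titer, neutralizing antibodies"; SAP III.A repeats it.

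The planned summaries are:
- SAP XI, incidence: "ADA and neutralizing antibodies results will be summarized by treatment at scheduled time point as well as all post-baseline visits". This gives counts and percentages by visit, plus one row pooled over the post-baseline visits.
- Protocol 9.4.3: "The incidence (number of subjects and percent) of a confirmed positive ADA response will be summarized by treatment".
- SAP XI, titers: summarized for subjects who turn antibody positive, with no definition of turning positive.
- SAP XI, hypersensitivity: early and delayed-type responses tabulated by treatment and by positive or negative ADA result, without saying at which time the result is taken.

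On sampling, SAP XI states: "Serum samples for the antibody assays will be collected at Day 1, 4, 7, 15, 30, 90 and EOS/180". The Day 1 sample is pre-dose. Protocol 4.1 says "There will be additional blood sample collection prior to IP administration for baseline myocardial biomarkers, PK, and immunogenicity assessment", and Protocol Table 15 places the Day 1 immunogenicity draw before the infusion. The general rule in SAP V.B is that "baseline is defined as the last non-missing measurement prior to study IP administration", but SAP XI does not apply it to ADA status.

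**The concern.** A positive antibody result after dosing has three possible origins: antibody induced by JK07, pre-existing antibody boosted by JK07, or pre-existing reactivity that has not changed. Only the first two are responses to the drug. The pooled post-baseline row, followed as written, adds all three together.

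The SAP treats other primary safety endpoints differently. TEAEs must start or worsen on or after the dosing day (VII.B). Laboratory and ECG results are given as change and shift from baseline (VII.C, VII.G). Arrhythmias are restricted to emergent ones (VII.H). The ADA incidence has no such contrast, although the sample that would allow it is collected.

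Two further tables depend on the missing definition. The titer table implies conversion while the incidence row does not, so the two may describe different subjects. The hypersensitivity table could be built on Day 1 status, any post-dose status or treatment-emergent status, and each could group the subjects differently. With 4 to 7 JK07 subjects per dose level, one subject changes how a dose group looks.

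**Working it through.** Neither document states an ADA rate, so there is no plan figure for it to reproduce. The one related figure is the maximum enrolment.

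**1. Group sizes (Protocol 1.1, Treatment Groups and Duration).**
- Unexpanded cohort: 1 sentinel + 3 randomized = 4 JK07, with 1 placebo.
- Expanded cohort: 1 sentinel + 6 randomized = 7 JK07, with 2 placebo.
- Five unexpanded cohorts: 5 × 4 = 20 JK07 and 5 × 1 = 5 placebo.
- Seven expanded cohorts: 7 × 7 = 49 JK07 and 7 × 2 = 14 placebo. The total is 49 + 14 = 63, which agrees with the stated maximum.

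The sentinel is counted with the JK07 subjects. SAP XI names no analysis population.

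**2. Effect of one persistent Day 1 positive.** Incidence as written = (persistent Day 1 positives + converters) / n. Treatment-emergent incidence = converters / n, where n is all evaluable subjects and no one is boosted.

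| JK07 subjects | Day 1 positive | Converters | As written | Treatment-emergent |
|---|---|---|---|---|
| 4 | 1 | 0 | 1/4 = 25.0% | 0/4 = 0% |
| 7 | 1 | 0 | 1/7 = 14.3% | 0/7 = 0% |
| 4 | 1 | 1 | 2/4 = 50.0% | 1/4 = 25.0% |
| 7 | 1 | 1 | 2/7 = 28.6% | 1/7 = 14.3% |

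Each such subject adds 25.0 or 14.3 percentage points.

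**3. How many Day 1 positives to expect.** The documents give no prevalence p of pre-existing reactivity, so 5-15% is an assumption. Expected number = p × N.
- N = 20: 0.05 × 20 = 1.0 to 0.15 × 20 = 3.0.
- N = 49: 0.05 × 49 = 2.45 to 0.15 × 49 = 7.35.

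These are subjects positive before dosing. Those miscounted are the subset who stay positive without a titer rise.

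**4. Chance that a given dose group contains at least one.** This is 1 − (1 − p)^n.

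| Assumed p | n = 4 | n = 7 |
|---|---|---|
| 5% | 1 − 0.95^4 = 18.5% | 1 − 0.95^7 = 30.2% |
| 10% | 1 − 0.90^4 = 34.4% | 1 − 0.90^7 = 52.2% |
| 15% | 1 − 0.85^4 = 47.8% | 1 − 0.85^7 = 67.9% |

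**5. Whether pooled placebo would reveal the background.** At an assumed 10%, five placebo subjects would show no positive with probability 0.90^5 = 59%. Pooled placebo numbers only 5 to 14.

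**The case against.** The strongest reply is that the plan already exposes background reactivity. Day 1 is a scheduled time point, so the by-visit table gives baseline prevalence in each group. Pooled placebo gives a second view, and the listings let a reader find any Day 1 positive among so few subjects. The endpoint is worded as presence of antibodies, which a plain count measures. No hypothesis is tested (Protocol 9.1), and neither document makes ADA incidence an escalation criterion. The table shells are a separate document (SAP I.B) and may already show baseline status.

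Much of this stands, and it limits the severity. It does not repair the pooled row: a group-level Day 1 percentage cannot be subtracted subject by subject, and reclassifying from listings is post hoc, whereas SAP I.B gives pre-specification as its purpose.

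A reader might infer four stronger points that the documents do not support:
- That the SAP rules that positives count whatever the Day 1 result. It is silent; the effect comes from an omission.
- That baseline prevalence goes unreported. The Day 1 row reports it.
- That the hypersensitivity table uses the pooled post-baseline status. The SAP does not say which status it uses.
- That neutralizing-antibody reporting conflicts with the protocol. SAP XI says "The serum samples for antibodies will be assayed for neutralizing antibodies", while Protocol 8.2.8 says "the confirmed positive samples will be reported and their potential for neutralizing activity will be explored". The SAP sentence does not say all samples, and its neutralizing percentages already take ADA-positive results at the visit as denominator. No reported percentage is shown to change.

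**Conclusion.** The concern holds in a limited form. As written, the overall post-baseline ADA incidence includes any subject positive before dosing who stays positive without a boost, and nothing in either document separates such subjects from true responders. The size per subject, 25.0 or 14.3 percentage points, follows from the design alone. The number affected does not. The estimate of about 1-3 of 20 to about 2-7 of 49 JK07 subjects positive before dosing rests on an assumed 5-15% prevalence, and its upper end requires all seven cohorts, each expanded to nine. It is a ceiling on miscounting, because Day 1 positives who lose positivity, or whose titer truly rises, are not miscounted. If pre-existing reactivity is absent, the two definitions give the same incidence. Since the analysis is descriptive, the consequence is a possibly misleading rate for a primary endpoint; no inferential error arises.

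**What to change.** Amend SAP XI before database lock:
- Define treatment-emergent ADA as Day 1 negative with a later confirmed positive, or Day 1 positive with a post-dose titer rise of at least a pre-set multiple (for example 4-fold).
- Use as denominator the subjects with an evaluable Day 1 result and at least one post-dose result.
- Apply this one status to the overall post-baseline incidence, the titer summary and the hypersensitivity table.
- Keep the by-visit rows, including Day 1, as planned. They already give baseline prevalence.

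This is a cheap improvement: SAP wording and matching table shells, using samples already scheduled. The downside is that the titer multiple has to be chosen and justified in advance.

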### **XIII. Changes from Protocol**

Per Protocol section 9.4.3 Safety Analyses, the incidence of treatment-emergent abnormal vital signs should be summarized using descriptive statistics. However, no abnormality flag for vital signs was collected, therefore no specific table or listing for abnormal vital signs will be produced.

Note that abnormal and clinically significant vital signs will be registered as adverse events, as mentioned in the Protocol section 8.3.7: “Any emergent laboratory abnormality (e.g., clinical chemistry or hematology) or other abnormal assessment findings (e.g., ECG or vital signs) that meets any of the following criteria should be recorded as an AE or SAE”.

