### 5.2 Exclusion Criteria

Subjects are excluded from the study if any of the following criteria apply:

1. Participating in any other study and have received any other investigational drug within 30 days prior to screening or 5-half-lives, whichever is longer, or any other investigational implanted device within 30 days prior to screening, or are taking part in a nonmedication study which, in the opinion of the Investigator, would interfere with study compliance or outcome assessments.
2. Any past participation in a study that has investigated the NRG-1 pathway (e.g., Neucardin, cimaglermin).

3. Heart failure due to hypertrophic cardiomyopathy, restrictive cardiomyopathy, arrhythmogenic right ventricular dysplasia (ARVD), stress-induced ("Takotsubo") cardiomyopathy, chemotherapy-induced cardiomyopathy, peripartum cardiomyopathy, infiltrative or inflammatory cardiomyopathies, and primary valvular disease.
4. Diagnosed with medically documented acute coronary syndrome within 3 months of screening or a medically documented acute myocardial infarction within 6 months of screening.
5. Cardiac surgery, coronary artery revascularization, percutaneous coronary intervention, or valvuloplasty within 3 months prior to screening.
6. Any subject who has received an indication for coronary revascularization within 3 months prior to screening.
7. Any major surgical procedure within 1 month prior to screening or planned surgical procedure during the study period.
8. Sustained systolic BP <90 mm Hg and/or diastolic BP <50 mm Hg (confirmed by a duplicate seated reading) on at least 3 consecutive readings (office) following informed consent and prior to randomization, or overt symptomatic hypotension defined as a decrease in systolic BP of 20 mm Hg or a decrease in diastolic BP of 10 mm Hg within three minutes of standing when compared with BP from the sitting or supine position or accompanied by dizziness, syncope, blurry vision.
9. Resting HR >100 beats per minute (bpm) at Screening (Visit 1) or prior to randomization which is sustained for >15 minutes in two episodes separated by one hour of observation except in sustained atrial fibrillation when HR of up to 110 bpm is acceptable.

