### **8.3.3      Time Period and Frequency for Collecting AE and SAE Information**

All AEs, including SAEs will be collected from the time of enrollment and until 30 days after the IP administration. Following the first 30 days, only SAEs deemed at least possibly related to the study drug or study procedures should be collected.

Medical occurrences that begin before the start of study treatment but after obtaining informed consent will be recorded on the Medical History/Current Medical Conditions section of the eCRF, not the AE section.

Investigators are not obligated to actively seek AEs or SAEs for subjects after their study participation ends. However, if the Investigator learns of any SAE, including a death, at any time after a subject has been discharged from the study, and he/she considers the event to be reasonably related to the study treatment or study participation, the Investigator must promptly notify the Sponsor.

All SAEs will be recorded on an SAE report form and reported to the Sponsor designee within 24 hours of the investigator's awareness of the event. The Investigator will submit any updated SAE data to the Sponsor

designee within 24 hours of the investigator's awareness of any follow-up information associated with the event.

SAE reports will be submitted to IQVIA Biotech Safety Management Department via one of the following methods:

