### **B. Purpose of the Statistical Analysis Plan**

This Statistical Analysis Plan (SAP) is based on the JK07.1.01 study Protocol Amendment 3.0, providing additional details concerning the statistical analyses outlined in the protocol and reflecting any changes to the protocol.

This SAP will govern the analysis of data from this study. This plan contains definitions of analysis populations, derived variables, data handling rules, format of data presentation and statistical methods for the safety, pharmacokinetic (PK), and pharmacodynamic (PD) analyses. The plan may be modified until the time of database lock. The database will be locked after medical/scientific review of the data has been completed, protocol deviations have been identified, and the data have been declared clean. The purpose of the SAP is to ensure the credibility of the study findings by pre-specified statistical approaches to the study data prior to the database lock. This plan will not repeat all the definitions given in the protocol but will provide further details of summaries and analyses planned therein. Any deviations from the analysis plan, including any after the time of database lock, will be documented as such in the study report. Table, Listing, and Figure (TLF) shells are provided in a separate, accompanying document. The SAP will take precedence over the protocol.

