### **D. Vital Signs**

Vital sign parameters, including the weight, body temperature, heart rate, respiratory rate, and systolic and diastolic blood pressure, will be summarized using descriptive statistics by cohort at each visit, by treatment group (and placebo) and overall. Absolute values and changes from baseline will be presented.

Vital signs will also be presented in a by-subject listing, detailed in result, unit, CFBL.

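### The SAP drops the protocol's incidence of treatment-emergent abnormal vital signs because no flag was collected, although it can be derived from the numeric values and adverse event reporting does not replace it

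*SAP*

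**What the plan says.** Protocol 9.4.3 (Safety Analyses) states: "The incidence of treatment-emergent abnormal laboratory, vital sign, and ECG values will also be summarized using descriptive statistics". This is in addition to the descriptive summaries of raw values and changes from baseline.

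The SAP, under Changes from Protocol, withdraws the vital-sign part and gives one reason: "no abnormality flag for vital signs was collected, therefore no specific table or listing for abnormal vital signs will be produced". It then points to AE reporting as the place where such findings will appear: "abnormal and clinically significant vital signs will be registered as adverse events". SAP I.B says "The SAP will take precedence over the protocol", so the withdrawal is operative.

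What remains for vital signs is in SAP VII.D. Weight, temperature, heart rate, respiratory rate and systolic and diastolic pressure are summarised by visit ("Absolute values and changes from baseline will be presented") and listed in full ("Vital signs will also be presented in a by-subject listing, detailed in result, unit, CFBL").

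On AE collection, Protocol 8.3.3 states: "Following the first 30 days, only SAEs deemed at least possibly related to the study drug or study procedures should be collected". SAP VII.B applies the same 30-day cut.

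**The concern.** The protocol treats abnormal values and AEs as two separate displays of the primary safety data. The SAP removes the first and relies on the second. The only reason given is that sites did not record a flag, but a flag is just one way of obtaining an incidence. When the measurement itself is in the database, the flag can be derived.

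This is a first-in-human study in patients with HFrEF. Protocol 2.3 cites the possibility of long-lasting cardiovascular effects as a reason for enrolling patients rather than healthy volunteers, and follow-up runs to Day 180. How many subjects on each dose had a low blood pressure or a high heart rate that was not there at baseline is a natural question. Under the SAP as written, no table answers it. A reader would have to count from the listing by hand, using cut-offs chosen after the data are known.

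**Working it through.** There is no power or sample-size figure to reproduce for this point. The check sets provisions side by side and counts scheduled assessments.

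**1. Can the incidence be derived without a flag?**
- Protocol 8.2.6: temperature, respiratory rate, heart rate and blood pressure are measured. The eCRF holds the average of three blood pressure readings per time point.
- SAP VII.D: all of these are presented as values and as changes from baseline, so they are numeric in the analysis data.
- SAP V.B defines baseline, so a value beyond a cut-off post-dose but not at baseline can be identified.
- SAP VII.G already counts subjects in QT and QTcF categories set by numeric cut-offs. SAP V.M allows continuous variables in general to be grouped into categories.

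The incidence is derivable. What is missing is a stated cut-off, not data.

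**2. Does AE reporting cover the same values?**
- Up to Day 30, Protocol 8.3.7 makes an abnormal vital sign an AE only if it comes with signs or symptoms, needs intervention, may need a change of therapy with an effect on study treatment, or is otherwise judged clinically significant by the investigator. Other abnormal values are not AEs.
- After Day 30, only serious AEs at least possibly related to study drug or procedures are collected (Protocol 8.3.3; SAP VII.B).

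**3. How much of the schedule falls after the AE cut?** (Protocol Table 1 and its ECG footnote; vital signs follow the ECG time points)
- By day: 1, 2, 3, 4, 7, 11, 15, 30, 60, 90, 135, 180 = 12 days. After Day 30: 60, 90, 135, 180 = 4. 4/12 = 33%.
- By time point: Day 1 at end of infusion, 0.5, 1, 2, 4 and 8 h (6); 24 and 48 h (2); Days 4, 7, 11, 15, 30 (5); Days 60, 90, 135, 180 (4). Total 6 + 2 + 5 + 4 = 17. 4/17 = 24%.
- Day 11 vital signs are waived if that visit is remote. The counts above are of scheduled assessments.

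**4. What do the retained visit summaries show?**
- Small cohort: 1 sentinel + 3 randomised = 4 JK07 subjects. One subject is 1/4 = 25 percentage points of incidence.
- Expanded cohort: 1 + 6 = 7 JK07 subjects. One subject is 1/7 = 14 percentage points.
- Illustration, assuming one subject falls 30 mm Hg and the others do not change: the mean moves 30/4 = 7.5 mm Hg or 30/7 = 4.3 mm Hg.
- The minimum or maximum shows the extreme value at a visit. It does not show how many subjects were beyond a limit, or whether the same subject recurs across visits.

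**The case against.** The strongest reply is that little is lost. Every value remains in the by-subject listing, and minimum and maximum remain in the visit summaries. With 4 to 7 JK07 subjects per cohort, a reader can count. The primary endpoint is change from baseline, which is fully reported. The study is descriptive, and the SAP discloses the change and its reason. All of this stands, and it limits the point to a missing tabulation.

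A second reply also stands. A reader might infer that the protocol already defines an abnormal vital sign, because exclusion criterion 8 contains "Sustained systolic BP <90 mm Hg and/or diastolic BP <50 mm Hg" and criterion 9 a resting heart rate above 100 bpm. The documents do not support that reading. These are eligibility rules with persistence and repeat-reading conditions, which one averaged blood pressure per time point cannot reproduce. Criterion 9 accepts up to 110 bpm in sustained atrial fibrillation, which needs rhythm data that are not among the vital-sign variables. Nothing in either criterion covers respiratory rate, temperature, high blood pressure or low heart rate. Neither document defines an abnormal vital sign for post-dose analysis.

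Neither reply rescues the stated reason. Lack of a definition is a reason to write one. A listing is not the incidence summary that Protocol 9.4.3 requires, and counting from it leaves the cut-off to be chosen after the data are seen.

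**Conclusion.** The point holds as a reporting gap. A protocol-required safety summary is withdrawn for a reason that does not prevent it, and the named substitute is narrower throughout and almost closed after Day 30. At 4 of 12 scheduled post-dose vital-sign days (4 of 17 time points), an abnormal value is not counted as an incidence anywhere unless it is part of a possibly related serious event. Before then, values that do not meet the Protocol 8.3.7 criteria are also untabulated, so the gap is not only a late one.

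Two stronger readings should be avoided. Late hypotension or tachycardia would not vanish from the report: the values stay in the listing and in the minimum and maximum, and possibly related serious events are still collected. Nor is a primary endpoint dropped: change from baseline in vital signs is unaffected.

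The day and time-point counts rest on the schedule in Protocol Table 1 being followed. The 30 mm Hg illustration is an assumption, not a prediction. The documents give no expected rate of abnormal values, so the number of subjects affected cannot be estimated.

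**What to change.** In the SAP's Changes from Protocol, delete the missing-flag rationale and reinstate the summary as a derived one. In SAP VII.D:

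- State an analysis cut-off for each vital sign, described as display-only and not as a clinical rule. Systolic <90 mm Hg, diastolic <50 mm Hg and heart rate >100 bpm may be borrowed from the eligibility criteria as single-reading cut-offs, stated as such and not as the protocol's definition of abnormality.
- For the remaining parameters and directions, state cut-offs or say how CTCAE v5.0, which SAP VII already applies to safety data, will be used.
- Tabulate the number and percentage of subjects beyond each cut-off post-dose but not at baseline, by treatment group and visit through Day 180.
- Flag those values in the existing by-subject listing.

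The cost is SAP wording, one table and a little programming, with no new data collection. Some flagged single readings will not be clinically significant, and the single-reading heart-rate cut-off ignores the atrial fibrillation allowance; a footnote should say both. SAP I.B allows changes until database lock. If lock has passed, the table can still be added and documented in the study report.
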